Effects of a 12-week supervised or home-based multicomponent training program on Psychological, and Physical variables in Fibromyalgia patients.

LABORATORY/DEPARTMENT

Laboratory of Exercise Science and Sport, Degree Program in Sports Science and Techniques, Department of Translational Biomedicine and Neurosciences (DiBraiN), University of Bari – Aldo Moro

EXPERIMENTAL DESIGN Interventional

EXPECTED START AND END DATE OF THE PROJECT March 2025 – May 2025

FUNDS USED FOR THE PROJECT No

DATE OF THE DOCUMENT 24/04/2025

SCIENTIFIC RATIONALE

Fibromyalgia (FM) is a chronic syndrome characterized by widespread musculoskeletal pain, fatigue, sleep disturbances, cognitive difficulties, and psychological distress. It predominantly affects women and has a significant impact on quality of life, daily functioning, and overall well-being. Despite its high prevalence and burden, the pathophysiology of FM remains complex and not fully understood, and current treatment strategies often require a multifaceted approach. Among non-pharmacological interventions, physical exercise is widely recognized as a cornerstone of FM management, with growing evidence supporting its efficacy in reducing symptoms and improving both physical and psychological outcomes.

A substantial body of research indicates that regular physical activity can help modulate pain perception, improve physical function, and alleviate emotional distress in individuals with FM (McLoughlin et al., 2011). Traditionally, aerobic training has been the most investigated form of exercise in this context, with several randomized controlled trials showing moderate benefits in pain reduction, fatigue, and depression (Tan et al., 2022). However, more recent studies suggest that multicomponent exercise programs—which combine aerobic, resistance, and flexibility training may produce superior outcomes compared to aerobic training alone (Albuquerque et al., 2022; Bidonde et al., 2019). These findings point to the importance of integrating different types of exercise to address the heterogeneous symptom profile associated with FM.

In parallel, the mode of delivering exercise interventions has also evolved. Remote or home-based exercise programs, especially those delivered via video or telehealth platforms, have demonstrated potential for improving accessibility and reducing barriers such as transportation, scheduling, and physical limitations (Serrat et al., 2022). Nonetheless, there is still limited evidence regarding the effectiveness and adherence to such programs when compared to traditional supervised training. Specifically, it remains unclear whether a structured, supervised multicomponent training program, compared to home-based sessions, can provide additional benefits in terms of clinical outcomes, psychological health, and program adherence.

The program is grounded in the guidelines provided by the American College of Sports Medicine (2018) and tailored to accommodate the specific needs and tolerances of patients with FM.

AIMS AND HYPOTHESES OF THE PROJECT

Primary outcome:

The purpose of this study is to evaluate the effectiveness of supervised MCT on physiological parameters, physical fitness, mental well-being, and quality of life in subjects with a history of FM, compared to a non-supervised home-based MCT protocol and a waitlist control group (WLCG).

Secondary outcome:

Assess the adherence through analysis of dropout rates and the number of completed sessions.

Hypothesis:

We hypothesize that both groups will report improvements in physiological parameters, physical fitness, mental well-being, and overall quality of life compared to the WLCG. Additionally, the supervised MCT group will show superior improvements in physiological parameters and adherence compared to the non-supervised home-based MCT group.

CHARACTERISTICS OF PARTICIPANTS

The study aims to recruit at least 30 individuals with a history of FM, aged between 30 and 75 years.

Inclusion Criteria

- Women/Men
- Diagnosis of fibromyalgia
- Age between 30 and 75 years at the time of initial treatment;
- Signature of a written informed consent form (or their legally recognized representatives must sign) indicating that the patient understood the purpose and procedures required for the study and is willing to participate in the study;
- Sedentary lifestyle (subjects who have not followed WHO guidelines for aerobic and resistance exercise in the past 3 months);
- Positive medical specialist assessment of noncompetitive physical activity practice;

Exclusion Criteria

- Expected absence for more than one week during the intervention period
- Absence of a medical certificate of suitability for non-competitive sports
- Severe musculoskeletal or joint disorders with significant mobility limitations
- Uncontrolled hypertension or untreated heart disease;
- Pshychiatric disorders;

SAMPLE SIZE

A priori power analysis (Kang, 2021) with a Type I error of 0.05 and Type II error rate of 0.10 (90% statistical power) calculated that 9 participants per group would be sufficient to observe moderate interaction effects between "Time x Group."

RECRUITMENT METHOD

Participants will be recruited through the Neurophysiopathology Unit, Polyclinic General Hospital, Bari; located at [name], and will be randomly assigned to one of three groups:

- Supervised MCT
- Non-supervised home-based IMCT
- WLCG

data collection

Before the intervention, all participants, with prior approval from their primary care physician, will sign an informed consent form. All participants will undergo physiological evaluations and functional tests before (T0) and at the end of the intervention (T1). Data will be collected anonymously, assigning each participant a random identification number.

Measurements:

Anthropometric Parameters:

- Height
- Weight
- BMI

Physical Parameters:

- Timed Up and Go (TUG)
- 30 Seconds Chair Stand Test (30"CST)
- 2 Minutes Step Test (TMST)
- Handgrip Strength Test (HGS)
- Back scratch test (BST)
- Arm Curl Test (ACT)
- Chair Sit&Reach Test (CSRT)

Psychological Parameters:

- Tampa Scale of Kinesiophobia (TSK)
- Pain Catastrophizing Scale (PCS)
- Toronto Alexithymia Scale (TAS 20)
- State Trait Anxiety Inventory (S.T.A.I.1-2)
- Physical Activity Enjoyment Scale (PACES)
- Beck Depression Inventory (BDI)
- Global Physical Activity Questionnaire (GPAQ)
- Brief Pain Inventory (BPI)
- Numeric Pain Rating Scale (NRS)
- Multidimensional Assessment of Fatigue Scale (MAF)
- Medical Outcomes Study Sleep Scale (MOS)
- Short Form Health Survey 36 (SF-36)
- Fibromyalgia Impact Questionnaire (FIQ)

Experimental Design

After initial evaluations, participants will be randomly assigned to one of the three groups. All protocols will last 12 weeks and take place at the Angiulli Artistic Gymnastics Society (Bari). Sessions will be conducted in small groups. These groups will be closely supervised by exercise professionals, specialists in adapted physical activity (AFA), to ensure participant safety, maintain proper intensity, and correct execution technique. To monitor and regulate training intensity (internal load) during sessions, the Borg Perceived Exertion Scale (RPE) (6-20) will be used at the end of each exercise set to regulate the load to Borg = 13-15 points (Gary Liguori & ACSM, 2021). Participants will be familiarized with the scale beforehand.

Participants in the WLCG will not perform any structured physical activity during the entire intervention period, maintaining their usual lifestyle and placed on a waiting list to receive adapted physical activity after the 24-week intervention period.

Supervised MCT protocol:

Each training session will include an initial muscle activation phase lasting 10 minutes (low-intensity walking, Borg = 10-11) to increase heart rate, improve muscle blood flow, and prepare the main joints for the subsequent work phase. This will be followed by a main 40-minute exercise period (aerobic exercise, mobility exercises, and resistance training) and a 10-minute cool-down period (breathing exercises and stretching).

The cardiorespiratory training will consist of progressive aerobic exercises: controlled and rhythmic jumping jacks, step-ups on a stable platform (such as a low step or a stable surface), alternating knee lifts, rapid lateral steps, or lateral leg raises. Finally, 3 minutes of low-intensity walking will facilitate recovery for the next training phase.

The mobility training will consist of specific exercises (thoracic extensions, cat-cow, overhead stretching with a stick, and active internal hip rotations) targeting the main joints. These will be performed to the maximum (1 to 3 sets) but avoiding pain. The duration will gradually increase from 30 to 60 seconds per repetition, repeating from one to three times. Rest intervals of 30 to 60 seconds will be provided between sets and exercises.

The resistance training will consist of exercises targeting different muscle groups (8 exercises): quadriceps (leg extension with ankle weights/half squat with a chair), biceps (unilateral dumbbell curl), shoulders (dumbbell shoulder press), triceps (dumbbell French press), chest (dumbbell chest press/dumbbell flyes), and back (dumbbell rows). The resistance training program will follow the principle of gradual progressive load. Initially, participants will perform one set of 10-15 repetitions, which will increase to three sets of 10-15 repetitions during the intervention. Load adjustments will

be made to ensure that the perceived effort (RPE) remains between 13 and 15 on the Borg Scale (6-20). During the protocol, participants will be given rest intervals of 60 to 120 seconds between sets and exercises. To prevent early muscle fatigue, exercises will be performed using an alternating training method based on muscle group division (upper body exercises will be performed in the first session and lower body exercises in the second).

The cool-down period will consist of breathing exercises and stretching. Stretching will be performed by seeking the maximum stretch on all the main muscle groups (1 to 3 sets per muscle group) while avoiding joint pain. The duration will gradually increase from 10 to 30 seconds per stretch, repeating from one to three times for a total of 60 seconds per exercise.

Non-supervised home-based MCT protocl:

Each will receive a personalized form via email, with exercises adapted to their level and progressively modulated in terms of intensity and duration consistent with what is proposed in the project, adapted to the individual physical capabilities detected in the initial phase. The protocol will be structured with the integration of joint mobility exercises, aerobic activity and resistance training at natural load or with small. Each session will be supported by video material that can be accessed through a dedicated link: by logging on, the participant would view a comprehensive guide with a detailed explanation of the exercises, accompanied by practical demonstrations, postural cues and suggestions for correct execution. After viewing the video, participants were invited to independently repeat the proposed exercises, respecting the directions regarding the number of repetitions (from 6-8 up to 10-12) and sets (2 or 3), depending on their fitness level and type of exercise.

Each training session, lasting about 60 minutes, was divided into three phases:

- Initial phase (warm-up and general activation ~10 minutes), light activity such as walking at a gentle pace will be proposed, aiming to activate muscles, gradually increase heart rate and mobilize major joints. The perceived intensity will be at a low level on the Borg scale (10-11).
- 2. Central phase (main work ~ 40 minutes) exercises with differentiated objectives such as Joint mobility: active and controlled movements aimed at improving range of motion in specific joints (e.g., thoracic spine, hips, shoulders), with progressive number of sets and duration o Aerobic activity: dynamic exercises performed free-body or with simple supports (e.g., step, stable chairs), such as alternating knee lifts, side steps or rhythmic movements involving upper and lower limbs, to stimulate cardiorespiratory capacity o Isometric exercises: muscle toning activities performed in static hold, targeting the major muscle groups (upper and lower limbs, trunk), with progression in the number of sets and duration of contraction. The resistance

training program will follow the principle of gradual and progressive loading. Initially, participants will perform one set of 10-15 repetitions, which will increase to three sets of 10-15 repetitions during the intervention. Load adjustments will be made to ensure that the perceived exertion (RPE) remains between 13 and 15 on the Borg scale (6-20). During the protocol, participants will have rest intervals of 60 to 120 seconds between sets and exercises. Intensity will be adjusted to maintain moderate perceived exertion, alternating between upper and lower body days to avoid overload. Final phase (cool-down ~10 minutes) the session will be concluded with a relaxation phase through video-guided breathing exercises and static stretching. Stretching exercises were performed for all major muscle groups, with progression in time of maintaining positions and attention to respecting individual limits (absence of pain or joint discomfort). The duration will gradually increase from 10 to 30 seconds per stretch, repeating from one to three times for a total of 60 seconds per exercise.

REFERENCES

- Albuquerque, M. L. L., Monteiro, D., Marinho, D. A., Vilarino, G. T., Andrade, A., & Neiva, H. P. (2022).
 Effects of different protocols of physical exercise on fibromyalgia syndrome treatment:

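### No primary endpoint, success rule or multiplicity rule: the primary outcome is a four-domain aim over 20 unranked instruments, so the 0.05, the 90% power and the 9 per group describe no named endpoint

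*Combined protocol and SAP*

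**What the plan says.** In the combined protocol and SAP, under Aims and Hypotheses, the Primary outcome entry is a purpose: "to evaluate the effectiveness of supervised MCT on physiological parameters, physical fitness, mental well-being, and quality of life". The comparators are the home-based programme and the waitlist control group (WLCG). It names no instrument, score or summary measure.

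The only Secondary outcome is "Assess the adherence through analysis of dropout rates and the number of completed sessions", so it ranks none of the clinical measures.

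The Hypothesis paragraph makes two predictions. First, "both groups will report improvements in physiological parameters, physical fitness, mental well-being, and overall quality of life compared to the WLCG". Second, "the supervised MCT group will show superior improvements in physiological parameters and adherence" relative to home-based training.

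The Measurements list gives three anthropometric measures, 7 physical tests and 13 questionnaires, all at T0 and T1. None is marked primary or key.

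The Sample Size section reports a power analysis "with a Type I error of 0.05 and Type II error rate of 0.10" and concludes that "9 participants per group would be sufficient to observe moderate interaction effects" of Time x Group. It gives no variable, numeric effect size or T0-T1 correlation. The document has no statistical analysis section, success criterion, hierarchy or multiplicity adjustment.

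**The concern.** An error rate and a power figure belong to a particular test of a particular variable. Here the only test mentioned is a Time x Group interaction on something unnamed, while the primary aim spans four domains and two comparators. The hypothesis joins the domains with *and*, but nothing says whether every instrument, one per domain, or any single one must succeed. Under the last reading, the headline instrument could be chosen from 20 after the results are known.

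A lesser point concerns the supervised-versus-home prediction. Its only clinical domain is physiological parameters, and no measurement heading carries that name. The title speaks only of a "multicomponent training program on Psychological, and Physical variables in Fibromyalgia patients". Until the intended measure is stated, that prediction cannot be scored.

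**Working it through.** **Inputs from the document.** 3 groups; 2 time points; 9 per group (N = 27); Type I error 0.05; power 90%; instruments 7 + 13 = 20 (height, weight and BMI not counted; the two-part anxiety inventory counted once).

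**Inputs assumed.** No true effect; 20 equally correlated change scores, correlation r = 0, 0.3, 0.5 or 0.7; one-way F test on change (equivalent to Time x Group with two time points); pooled-variance contrasts at two-sided 0.05, counted only in the favourable direction.

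**The plan's own figure.** The 9 per group cannot be reproduced, because endpoint, effect size and correlation are missing. As an illustration, take moderate as f = 0.25. The noncentrality is λ = N·f²·2/(1 − ρ), with 2 and 24 degrees of freedom and ρ the T0-T1 correlation:
- ρ = 0.77: λ = 27 × 0.0625 × 2 / 0.23 = 14.67, power 90.6%.
- ρ = 0.5: λ = 27 × 0.0625 × 2 / 0.5 = 6.75, power 58%.

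So 9 per group is attainable under some values and not others. Because ρ depends on the instrument, the 90% cannot be checked until one is named.

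**Error rate without a rule.** For independent outcomes, the chance of at least one significant interaction is 1 − 0.95^20 = 64%, with 20 × 0.05 = 1 false positive expected. Simulation extends this to correlated outcomes and to directional claims. *Gated* means that contrasts count only after a significant omnibus test on the same instrument. The protocol states no such gate, so both versions are shown (%).

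| What counts as success | r = 0 | 0.3 | 0.5 | 0.7 |
|---|---|---|---|---|
| Any significant Time x Group test, any direction | 64 | 56 | 44 | 31 |
| Any instrument, either programme over WLCG, gated | 35 | 27 | 21 | 15 |
| Same, ungated | 60 | 44 | 34 | 24 |
| Any instrument, both programmes over WLCG on that instrument, gated | 9 | 7 | 6 | 4 |
| Any instrument, any of three directional contrasts, gated | 45 | 36 | 28 | 20 |
| Same, ungated | 74 | 58 | 46 | 34 |
| One instrument in each of three domains, split 7/2/11, gated | 0.1 | 0.8 | 1.4 | 2.1 |
| Same, ungated | 0.9 | 3.0 | 4.2 | 4.9 |
| One instrument in each of three domains, split 7/6/7, gated | 0.2 | 1.5 | 2.6 | 3.1 |
| Same, ungated | 1.8 | 5.2 | 7.1 | 7.3 |
| All 20 instruments | <0.1 | <0.1 | <0.1 | <0.1 |

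Simulation error is a few tenths of a point at most. Supervised over WLCG or supervised over home, which is the pair in the Primary outcome entry, gives about the same rates as either programme over WLCG.

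The domain rows use either programme over WLCG and leave out the unmapped physiological domain. The splits are fitness / quality of life / mental well-being. The first puts only SF-36 and FIQ in quality of life; the second adds BPI, NRS, MAF and MOS. The protocol maps no questionnaire to a domain, so neither split is an upper bound.

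For comparison, on one named instrument the gated chance of either programme over WLCG is 2.1%.

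**The case against.** The strongest reply is that this is a small trial whose hypothesis asks for improvement in all the domains together. A joint requirement is conservative, and the strict rows of the table bear that out. That stands as far as it goes: a reader should not infer that the trial carries a 45% or 74% false-positive rate. The any-one reading is an assumption, and the document does not say the sponsor will use it. Nor does it say the opposite, and the strict reading is just as unstated.

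The rows counting all three contrasts on all 20 instruments also need care. The hypothesis predicts supervised over home only for physiological parameters and adherence, and the Primary outcome entry does not include home over WLCG. Those rows are therefore wider than either statement and mark an outer limit. The rows for either programme over WLCG are closer to the text.

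Two further inferences are not supported. One is that 9 per group is wrong: its inputs are undisclosed, and at f = 0.25 with correlation 0.77 it gives 90.6%. The other is that no listed measure could be physiological: the anthropometric heading is a possible reading, and the data collection paragraph uses the word loosely.

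Treating PACES and GPAQ as process measures leaves 18 instruments and changes little. The 45/36/28/20% row becomes 42/33/27/19%.

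**Conclusion.** The concern holds. The plan names no primary endpoint, success rule, testing order or multiplicity rule, and its 0.05, 90% power and 9 per group refer to a Time x Group test on an unnamed variable. As written, nothing holds the 0.05 for the primary aim: under no effect, at least one of the 20 interaction tests is significant with probability 64/56/44/31%.

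The chance of a false claim of effectiveness runs from below 0.1% to about 74%. For either programme over WLCG on any one instrument it is 15 to 35% gated and 24 to 60% ungated. These figures rest on the assumed equal correlations and on 9 per group. The finding is that an unstated rule decides where in the range the trial falls, not that any one of these rates is the trial's own.

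This must be fixed, because until it is, no result can confirm or refute the primary aim. The unclear meaning of physiological parameters is a lesser, separate gap.

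**What to change.** Issue a dated amendment, before outcome data are examined, that does the following:

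1. Names one already-collected instrument and score, change from T0 to T1, as primary. The choice is the sponsor's.
2. States the success rule: which of supervised vs WLCG, supervised vs home and home vs WLCG must be significant to claim effectiveness.
3. Adopts one error-control device. Either the omnibus Time x Group test at 0.05 followed by pairwise contrasts at two-sided 0.05 (sufficient for three groups; simulated familywise error 0.050 to 0.051), or a pre-stated fixed order of contrasts at two-sided 0.05 (at most 0.051). Using both is needlessly strict, with 0.026 under the global null.
4. Makes the other 19 instruments secondary or exploratory, with 95% confidence intervals and no confirmatory claim unless adjusted.
5. States which listed measure physiological parameters means.
6. States that the 9 per group and 90% power apply to the Time x Group test on the named endpoint.

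The document is dated 24/04/2025, inside the March to May 2025 project window. If outcome data have already been seen, the choice must be reported as post hoc.

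**Cost.** No new measurements are needed, but the other 19 instruments can no longer support a primary claim. In a fixed order, power depends on a contrast's place. With assumed f = 0.25, T0-T1 correlation 0.77 and evenly spaced group effects, supervised vs home has about 45% power if tested second after supervised vs WLCG, the same as by the omnibus route, and 14% if tested last. At correlation 0.5 these become 22% and 2%. The loss comes from the order, not from the choice of device.

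### No analysis model is stated and only Time x Group is named; making ANCOVA on T0 the main analysis is a nearly free but modest gain in precision

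*Combined protocol and SAP*

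**What the plan says.** The document has no statistical analysis section. It names no model, covariate, contrast or baseline adjustment. Its one analytic term stands in SAMPLE SIZE, which "calculated that 9 participants per group would be sufficient to observe moderate interaction effects between" time and group, with a Type I error of 0.05 and 90% power. It gives no numeric effect size and no T0-T1 correlation.

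Two design features bear on the choice of model:

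- Two time points, under data collection: "All participants will undergo physiological evaluations and functional tests before (T0) and at the end of the intervention (T1").
- Baseline before allocation, under Experimental Design: "After initial evaluations, participants will be randomly assigned to one of the three groups".

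The hypotheses in AIMS AND HYPOTHESES OF THE PROJECT are pairwise. One is that "both groups will report improvements in physiological parameters, physical fitness, mental well-being, and overall quality of life compared to the WLCG". The other is that "the supervised MCT group will show superior improvements in physiological parameters and adherence compared to the non-supervised home-based MCT group". CHARACTERISTICS OF PARTICIPANTS sets the target: "The study aims to recruit at least 30 individuals", which is 10 per arm if allocation is equal.

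**The concern.** If the effect used for sample size is also the analysis, the trial would compare changes from T0 across three arms. A change score fixes the T1-on-T0 slope at 1. When the true slope is below 1, this over-corrects for baseline and adds noise. ANCOVA estimates the slope from the data.

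The stakes are precision in a trial of 27 to 30 people, using a T0 value that is collected anyway. An omnibus Time x Group test also does not give the estimates that the hypotheses need. With no model named, the choice between change score, T1 alone and adjusted T1 could be made after results are seen.

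**Working it through.** **Inputs from the document.** Alpha 0.05, power 0.90, 9 per group, three groups (N = 27), two time points.

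**Assumptions.** Rho from 0.3 to 0.95; Cohen's f = 0.25 where moderate is given a number; equal T0 and T1 variances unless stated; 1:1:1 allocation; complete data.

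**Step 1. The plan's own figure.** For the interaction with three groups and two times, the noncentrality is lambda = f² × N × 2/(1 − rho), with 2 and N − 3 = 24 degrees of freedom. Power of 90% needs lambda = 14.39. The 9 per group cannot be reproduced from the document alone, because f and rho are missing. With f = 0.25:

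- 0.0625 × 27 × 2 = 3.375, so 1 − rho = 3.375/14.39 = 0.235 and rho is about 0.77.
- At rho 0.5, lambda = 3.375/0.5 = 6.75 and power is 58%.

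Turned round, f = √(14.39 × (1 − rho)/54). The f that 90% power requires is 0.43, 0.37, 0.28 and 0.25 at rho 0.3, 0.5, 0.7 and 0.77.

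**Step 2. When ANCOVA is more precise.** Take the T0 SD as 1 and the T1 SD as s.

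- Change-score variance: s² + 1 − 2·s·rho
- ANCOVA residual variance: s²(1 − rho²)
- Difference: (1 − s·rho)²

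The gain therefore vanishes as the slope s·rho approaches 1. Against it stands the cost of estimating the slope: one error degree of freedom and an expected variance inflation of 1/(N − 5), which is 1/22 = 4.5% at N = 27 and 1/25 = 4.0% at N = 30.

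With s = 1 the variance ratio of ANCOVA to change score is (1 + rho)/2 × 23/22. This equals 1 at rho = 2 × 22/23 − 1 = 0.91.

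**Step 3. Power if the stated 90% holds.** Lambda is held at 14.39 for the change-score test. Figures are simulated with 9 per arm and equally spaced arm effects (100,000 runs; 200,000 at rho 0.95), so they include the cost in Step 2.

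| rho | f needed | Change score | ANCOVA |
|---|---|---|---|
| 0.3 | 0.43 | 90.2% | 97.8% |
| 0.5 | 0.37 | 90.0% | 95.6% |
| 0.7 | 0.28 | 89.8% | 93.0% |
| 0.77 | 0.25 | 90.0% | 91.9% |
| 0.9 | 0.16 | 90.0% | 90.1% |
| 0.95 | – | 90.0% | 89.3% |

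Both tests reject 4.9 to 5.1% of the time under the null.

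**Step 4. Unequal variances, change score still at 90%.**

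- s = 1.25: ANCOVA gives 94.7%, 91.6%, 88.9%, 88.4% and 88.5% at rho 0.3, 0.5, 0.7, 0.77 and 0.8. At rho 0.9 the variances are 1.5625 + 1 − 2.25 = 0.3125 and 1.5625 × 0.19 × 23/22 = 0.310, which is break-even.
- s = 0.8: ANCOVA gives 99.5%, 98.9%, 98.0% and 97.9% at rho 0.3, 0.5, 0.7 and 0.77.

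**Step 5. The pairwise contrasts.** The 95% CI half-width at 9 per arm is t × √variance, with variance 2(1 − rho)(2/9) for change scores and (1 − rho²)(2/9)(23/22) for ANCOVA. In SD units:

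- rho 0.5: 2.064 × √0.2222 = 0.97 against 2.069 × √0.1742 = 0.86.
- rho 0.77: 2.064 × √0.1022 = 0.66 against 2.069 × √0.0946 = 0.64.

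**The case against.** **This is a preference, not a defect.** The change-score test is valid, and baseline adjustment is neither planned nor excluded. That stands. A reader might infer that the plan commits to an inefficient analysis, or that its test is wrong. The document supports neither: Time x Group appears only as the effect powered for.

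**The comparator is inferred.** A Time x Group mixed model with a common baseline mean has essentially the efficiency of ANCOVA, so the loss may not arise. This also stands. The equivalence with change scores holds for a standard repeated-measures ANOVA, or for separate baseline means with complete data. It is a reason to name the model, since the present wording allows either.

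**The 8-point end does not fit a moderate effect.** Correct. At rho 0.3, 90% power with 9 per group needs f of about 0.43. Under f = 0.25 the gain at lower rho is larger (58% against 69% at rho 0.5; 44% against 60% at rho 0.3). There, however, the stated 90% is not met, and the low starting power is a separate sample-size matter. It should not be counted as a benefit of ANCOVA.

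**The sign is uncertain.** In part. If T1 is more variable than T0 so that the slope is near 1, ANCOVA loses 1 to 2 points. More variable T1 alone does not decide it: at an SD ratio of 1.25 ANCOVA still gains at rho 0.3 and 0.5.

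**Conclusion.** The point holds as one of efficiency. The document states no model, and the only effect it names implies a change-score comparison under the usual fit. ANCOVA on T0 targets the same effect because T0 precedes randomisation.

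If the stated 90% is true and variances are equal, the gain runs from about 8 points at rho 0.3 to about 2 at rho 0.77, and to none near 0.9. The gain that fits all the stated figures, with moderate read as f = 0.25, is about 2 points. With a T1 SD 1.25 times the T0 SD, about 1 to 2 points are lost from rho of about 0.7 to a little below 0.9.

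Rho, f and the variances are all assumptions. A reader might infer that the 90% claim is false. The document does not settle that, because it gives neither f nor rho. Nor does the gain show that every pairwise hypothesis becomes adequately powered.

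**What to change.** Add a short analysis paragraph:

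- For each continuous outcome measured at both T0 and T1, the main analysis is an ANCOVA of the T1 value on randomised group (three levels), with that outcome's T0 value as covariate and a common slope.
- Report adjusted differences with 95% CIs for supervised against WLCG, home-based against WLCG, and supervised against home-based.
- Keep Time x Group as a sensitivity analysis.

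The adherence aim ("Assess the adherence through analysis of dropout rates and the number of completed sessions") has no T0 value and falls outside this model.

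The document is dated 24/04/2025, after the expected March 2025 start, so data collection may already have begun. The paragraph should be fixed before any T1 data are analysed.

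The change needs no new data, visits or participants. Its statistical price is one error degree of freedom and 4 to 4.5% variance inflation at N = 30 to 27. The choice of primary outcome, multiplicity and the handling of missing T1 values are separate points that ANCOVA does not settle.
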